11.7. Subjects who are monitored on LATITUDE

For subjects who are remotely monitored, the wireless LATITUDE[™] Patient Management system will be utilized to collect and store treated tachyarrhythmia episodes. Alerts, diagnostic data, and all treated ventricular episodes EGMs are collected for endpoint evaluation directly from the LATITUDE database. Applicable reports will be uploaded remotely into the study database from the LATITUDE BSC team as defined on the data collection schedule on Table 11.1-2.

After programming to treatment arm (Index procedure Day 0), subjects who are remotely monitored with the LATITUDE system must have the following yellow alerts programmed on in the LATITUDE database:

- Ventricular shock therapy delivered to convert arrhythmia
- Accelerated ventricular arrhythmia episode
- Atrial Arrhythmia burden of at least {>1, 3, 6, 12, 18, or 24} hours in a 24 hour period
- Patient triggered event stored

If the HeartLogic feature is available in the implanted device, all subjects with this feature will be monitored by the LATITUDE BSC team for the specific HeartLogic alerts. In the event of an alert, a report will be uploaded by the LATITUDE BSC team into the study database.

Table 11.7-1: LATITUDE Follow Up Data – Device Report Upload

Data Collection Requirement	Retention of Original Source Documentation
LATITUDE Nominal Device ReportVentricular arrhythmia episodesLATITUDE Alerts	Reports uploaded into the study database by BSC LATITUDE team

11.7.1. Phone Call Visits for Subjects ON LATITUDE

Subject phone call visits are required in conjunction with the LATITUDE data device report upload visit. The data to be collected at the subject phone call visit include:

- An assessment of cardiac medication changes
- An assessment of reportable adverse events
- An assessment of device deficiencies

Source data requirements at the subject phone call visits for subjects who are monitored on LATITUDE are described in Table 11.7-2.

Table 11.7-2: Source Documentation Requirements: Subject Phone Call Visit

Da	ata Collection Requirement	Retention of Original Source Documentation
•	Reportable Adverse Events, Device Deficiencies, and Protocol Deviations, if applicable	Investigational Center
•	Cardiac Medication Changes	

11.7.2 Annual Follow-Up Visits for Subjects monitored on LATITUDE

For subjects monitored on LATITUDE, annual in-clinic visits are required to be performed per the data collection schedule on Table 11.1-2.

Tasks to be performed at the annual in-clinic follow-up visits include:

- Pulse generator interrogation with routine lead evaluation on implanted RA and RV leads which includes:
 - o Intrinsic sensing (mV)
 - o Pacing impedance (Ω)

- \circ Shock lead impedance (Ω)
- o Pacing threshold (V) (pulse width at physician discretion)
- Arrhythmia logbook evaluation
 - o Print applicable arrhythmia episodes
- Save interrogation session to USB
- Upload into EDC system

Table 11.7-3: Source Documentation Requirements: Annual Follow Up Visits for Subjects on LATITUDE

Data Collection Requirement	Retention of Original Source Documentation
Reportable Adverse Events, Device Deficiencies, and Protocol Deviations, if applicable	Investigational Center
Cardiac Medication Changes	
 Device Follow Up Report Selected Episode Electrograms, as applicable Device Settings Report Settings Change Report Arrhythmia log book 	Printed Copy of all final reports retained at Investigational Center Save to USB for Investigational Site. Copy will be sent to sponsor, if applicable Upload USB into EDC system

11.8. Unscheduled Visits: ICD Interrogation and Evaluation after ICD therapy

After a patient reports ICD therapy, an in-clinic visit must be scheduled within 30 calendar days, or as soon as possible. The following is required to be collected at all unscheduled inclinic visits:

- Ventricular arrhythmia episodes
- Reportable adverse events
- Medication changes

- Device programming changes
- Protocol deviations
- Device Deficiencies

Tasks to be performed at the unscheduled visit include:

- Pulse generator interrogation with routine lead evaluation on implanted RA and RV leads which includes:
 - o Intrinsic sensing (mV)
 - o Pacing impedance (Ω)
 - \circ Shock lead impedance (Ω)
 - o Pacing threshold (V) (pulse width at physician discretion)
- Arrhythmia logbook evaluation
 - o Print applicable arrhythmia episodes
- Save interrogation session to USB
- Upload into EDC system

Table 11.8-1: Source Documentation Requirements: Unscheduled Visits: ICD Interrogation and Evaluation after ICD therapy

Data Collection Requirement	Retention of Original Source Documentation
• Reportable Adverse Events, Device Deficiencies, and Protocol Deviations, if applicable	Investigational Center
Cardiac Medication Changes	
 Device Follow Up Report Selected Episode Electrograms, as applicable Device Settings Report Settings Change Report Arrhythmia log book 	Printed Copy of all final reports retained at Investigational Center Save to USB for Investigational Site. Copy will be sent to sponsor, if applicable Upload USB into EDC system

For subjects remotely monitored on LATITUDE:

If the LATITUDE database shows an alert related to a treated episode and/or the subject reports a treated episode, it will be at the Investigator Discretion, per their SOC if they want to bring the subject in to be seen for an unscheduled visit. The treated episode will be collected via the LATITUDE system and uploaded into the study database by the LATITUDE BSC team.

If the center does not bring the patient in for a treated episode as their standard of care practice, the coordinating Investigational center needs to call the patient to evaluate:

- Cardiac medication changes
- Reportable adverse events
- Device deficiencies

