MADIT-RIT⁸: The MADIT-RIT study was designed to test whether inappropriate shocks in primary prevention patients could be reduced through at least one of two treatment strategies when compared to a third control arm consisting of patients with conventional programming: increasing the rate cutoff (high rate therapy) or prolonging the time before delivering device therapy (delayed therapy). Patients were enrolled in MADIT-RIT from September 2009 through October 2011 and were followed for a mean of 1.4 years and the use of both CRT-D devices (50%) and ICDs (50%) were permitted. Both strategies were successful in reducing the risk of occurrence of first inappropriate ICD therapy, with high rate therapy associated with a 79% reduction (p<0.001) and delayed therapy associated with a 76% reduction (p<0.001). Furthermore, MADIT-RIT demonstrated that both programming strategies can be employed without increasing all-cause mortality or syncope.

Examination of appropriate ATP delivered in MADIT-RIT revealed 446 episodes in the convention programming arm, compared to 113 episodes in the high rate therapy arm and 143 episodes in the delayed therapy arm. The authors noted that this finding suggests that much of the ATP delivered in the conventional programming arm was prematurely delivered for non-sustained ventricular tachyarrhythmias. The delivery of ATP in these instances, while consistent with the programming of the device may also be clinically unnecessary.

PainFREE Rx II⁹: PainFREE Rx II, preceded by the PainFREE Rx¹⁰ pilot study, was designed to determine whether fast VT, defined as ventricular rhythms detected between 188-250 bpm, could be successfully and safely treated with ATP. The primary outcome measure was ATP effectiveness. This study enrolled patients from January 2001 to March 2002 and included a mix of patients with secondary indications and MADIT indications but ceased enrollment prior to the availability of ICD indications for the MADIT II and SCD-HeFT populations. Patients were randomized to two arms: one arm received ATP for fast VT with detection of 18/24 fast intervals with a rate cutoff of 188 bpm while the other arm was randomized to shocks only using the same rate cutoff of 188 bpm. After 11 months of follow-up, ATP was found to have successfully terminated 229/284 episodes of fast VT (81% unadjusted, 72% after adjusting for multiple events) and it was considered to be safe in

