11.1. Data Collection

The data collection schedule for this study is aligned with standard of care (SOC) practices at centers. Therefore, there are two data collection schedules for subjects: 1.) Subjects who are not monitored on LATITUDE and 2.) Subjects who are monitored on LATITUDE.

Table 11.1-1 for subjects who are NOT monitored on LATITUDE

Table 11.1-2 for subjects who are monitored on LATITUDE

Table 11.1-1 Data Collection Schedule – Subjects NOT on LATITUDE

Procedure/ Assessment	Enrollment (≤ 60 calendar days post successful implant)	Randomizatio n (Obtained day of device programming to assigned treatment arm)	Programing to Assigned Treatment Arm (Day 0) (Day of randomization. Cannot exceed 60 calendar days post implant)	Follow Up Visits through 5 years 6 Mo: 180±60 d 12 Mo: 360±60d 18 Mo:540±60d 24 Mo: 720±60 d 30 Mo: 900±60d 36 Mo: 1080±60d 42 Mo: 1260±60 d 48 Mo: 1440±60d 54 Mo: 1620±60d 60 Mo: 1800+30d	Unscheduled Visits (within 30 calendar days of therapy delivery)
Informed consent process, including informed consent signature and date	X				
Inclusion/Exclusion	X	♦			
ECG Upload—Standard of Care (recommended not required)			SOC		
Physical assessment			X		
Demographics	X				
Medical History			X		
Cardiac Medications			X	X**	X**
Randomization – obtained via the EDC system/Risk Stratifiers		X			
Device Interrogation/ Programming Status			X	X	X
Reportable AE's		*	*	*	*
Arrhythmia Episodes		*	*	*	*

Legend: X= Required; *=Data required only if the event occurred; SOC=Recommended if Center Standard of Care, **= Need to document changes to cardiac meds only, ◊= Sites must verify subject still meets inclusion/exclusion criteria prior to randomization

Table 11.1-2 Data Collection Schedule – Subjects ON LATITUDE

Study Reference Number C1924

Confidential

Procedure/Assessment	Enrollment (≤60 calendar days post implant)	Randomization (Obtained day of device programming to assigned treatment arm)	Programing to Assigned Treatment Arm (Day 0) (Day of randomization. Cannot exceed 60 calendar days post implant)	LATITUDE Follow Up Data (Automatic Device Report Upload) Done by Sponsor 6 Mo: 180±60 d 18 Mo:540±60d 30 Mo: 900±60d 42 Mo: 1260 ±60 d 54 Mo: 1620 ±60 d	Subject Phone Call Visit Done by Center 6 Mo: 180±60 d 18 Mo:540±60d 30 Mo: 900±60d 42 Mo: 1260 ±60 d 54 Mo: 1620 ±60d	Follow Up Visits (In Clinic) 12 Mo: 360±60d 24 Mo: 720±60 d 36 Mo: 1080±60d 48 Mo: 1440 ± 60d 60 Mo: 1800+30d	Unscheduled Visits (per Physician Discretion as SOC)

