19.1. Reportable Events by investigational site to Boston Scientific

It is the responsibility of the investigator to assess and report to BSC any event which occurs in any of following categories:

- All Serious Adverse Events
- All Device Related Adverse Events
 - PMT does not have to be reported unless the patient is symptomatic and it is true PMT. Document if there was a change in programming related to the PMT.
 - o Bradycardia only to be reported if the subject is symptomatic to the bradycardia
- All Serious Adverse Device Events
- All Device Deficiencies
- Unanticipated Adverse Device Effects/Unanticipated Serious Adverse Device Effects
- All Arrhythmic Related Events:
 - o Any treated or untreated ventricular event if not already documented as:
 - A sustained ventricular episode in the monitoring zone
 - SAF
 - A new onset of an atrial event not reported in the Medical History
 - ATR episodes do not need to be reported if it is a response to a known and/or previously reported atrial arrhythmia
- Syncope

- o Including reports of near syncope, which could include but not limited to symptoms of dizziness, lightheadedness, fainting
- For subjects with a HeartLogic Alert, any change in heart failure therapy which requires IV treatment should be reported as an AE.
- New findings/updates in relation to already reported events

For Event reporting the medical diagnosis must be reported. In case the diagnosis is not available, individual symptoms can be reported to fulfill reporting timelines. If a diagnosis becomes available at a later stage, it must be added to the reported event.

If it is unclear whether or not an event fits one of the above categories, or if the event cannot be isolated from the device or procedure, it must be submitted as an adverse event and/or device deficiency.

Any AE event required by the protocol, experienced by the study subject after informed consent and once considered enrolled in the study (as defined in study subject classification section), whether during or subsequent to the procedure, must be recorded in the eCRF.

Underlying diseases are not reportable as AEs unless there is an increase in severity of frequency during the course of the investigation. For centers in Austria cancer must always be reported as a Serious Adverse Event. Death events itself are not be recorded as an SAE, but must be reflected as an outcome of ONE (1) specific SAE/ SADE or USADE (see Table 20.2-1 for Event definitions).

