21.1. Data Monitoring Committee

An Independent Data Monitoring Committee (DMC) will meet periodically, or as needed, to review the results of the trial and to evaluate any safety issues that may arise during the course of the study. The DMC will include leading experts in Electrophysiology, who are not participating in the APPRAISE ATP study, and have no affiliation with BSC. The DMC will inform the study Principal Investigator on any safety concerns and other trends that would warrant modification or termination of the study. Responsibilities, qualifications, membership, and committee procedures are outlined in the DMC Charter.

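### For subjects on LATITUDE, no required alert covers an episode ended by ATP alone, so non-serious syncope and near-syncope may be found sooner, and possibly more often, in the shock-only arm

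*Combined protocol and SAP*

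**What the plan says.** Section 11.8 opens with a rule that is not limited to shocks: "After a patient reports ICD therapy, an in-clinic visit must be scheduled within 30 calendar days, or as soon as possible". In Table 11.1-1 (subjects not on LATITUDE) the unscheduled-visit column is headed "within 30 calendar days of therapy delivery". For subjects on LATITUDE the condition is "If the LATITUDE database shows an alert related to a treated episode and/or the subject reports a treated episode". The investigator then decides whether to see the subject. If not, "the coordinating Investigational center needs to call the patient to evaluate" medication changes, reportable adverse events and device deficiencies.

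Section 11.7 lists four alerts that must be on: "Ventricular shock therapy delivered to convert arrhythmia", an accelerated ventricular episode, an atrial arrhythmia burden threshold, and a patient-triggered stored event. None is for an episode that ATP ends.

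ATP is on in Zone 2 in Arm 1 (ATP and shock) and off in Arm 2 (shock only), per Tables 11.5-1 and 11.5-2. Section 19.1 makes syncope reportable, "Including reports of near syncope, which could include but not limited to symptoms of dizziness, lightheadedness, fainting", without requiring that it be serious. Reportable adverse events are also assessed in both arms about every six months, by phone or in clinic (Sections 11.6, 11.7.1 and 11.7.2).

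**The concern.** The prompt adverse-event contact is easier to set off after a shock than after successful ATP, and only one arm has ATP. If ATP averts shocks, more treated episodes in Arm 2 are followed by someone asking about symptoms soon afterwards. More dizziness and fainting could then be recorded in Arm 2 with no difference in what subjects experience.

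Syncope is a measure by which the Introduction judges the safety of earlier programming strategies, and Section 18.1 names delayed therapy as an added risk of this study. Section 21.1 asks the data monitoring committee "to evaluate any safety issues that may arise during the course of the study" and to report concerns or trends that would warrant changing or stopping the trial. A committee shown an excess of symptoms in Arm 2 could not tell a true excess from a detection difference. Whether ATP averts shocks is the question under test, so the plan cannot assume equal shock rates in order to keep ascertainment balanced.

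**Working it through.** **1. Routes to a prompt contact, subjects on LATITUDE (Sections 11.7 and 11.8).**

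| Route | Episode ended by a shock | Episode ended by ATP alone, no acceleration |
|---|---|---|
| Required shock alert | yes | no |
| Required acceleration alert | if it accelerated | no |
| Required patient-triggered alert | if the subject triggers it | if the subject triggers it |
| Subject reports therapy | if reported | if reported |
| Alert not required by the plan | possible | possible |

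Only the first two rows distinguish the arms by design. The scheduled phone call does not close the gap: its column in Table 11.1-2 has no arrhythmia-episode entry, and Section 11.7.1 gives it no episode review. Six-monthly windows of ±60 days allow successive contacts up to (360 + 60) − (180 − 60) = 300 days apart.

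**2. The plan's own figure, to fix the meaning of the shock rate.** Section 12.1.1.2 gives 6% or 7% without a time unit. Events needed for two one-sided tests with 90% power: d = 4 × [(z(0.978) + z(0.95)) / ln 0.65]² = 4 × [(2.014 + 1.645) / 0.4308]² ≈ 289, using the final level of 0.022 from Section 12.3.1. With 42 months of uniform accrual, exponential shocks and 10% attrition at 18 months, an 18-month reading of the rate gives N = 2604 (scenario 1) and 2591 (scenario 2), against the planned 2600. An annual reading gives about 418 events at 2600 subjects in scenario 1 and a required N of about 1740 to 1795, so it does not reproduce 2600. I use the 18-month reading.

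**3. Subjects with at least one shock-triggered contact.** Inputs: 1300 per arm; scenario 1; Arm 1 hazard λ = −ln(0.94)/1.5 = 0.0413 per year; attrition η = −ln(0.9)/1.5 = 0.0702 per year; follow-up f uniform on 1.5 to 5 years. Expected number = 1300 × mean of [λ/(λ+η)] × [1 − exp(−(λ+η)f)]. Everyone is treated as being on LATITUDE, because the share is not given.

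| Hazard ratio, Arm 2 vs Arm 1 | Arm 1 | Arm 2 | Excess |
|---|---|---|---|
| 1.00 | 144 | 144 | 0 |
| 1.25 | 144 | 177 | 33 (2.5% of the arm) |
| 1.54 | 144 | 214 | 70 (5.4%) |

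On the annual reading the excess is 0, 46 and 96.

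**4. Apparent ratio (Arm 2 / Arm 1) when true symptom rates are equal.** The documents give no capture rates, so these are assumptions: p = share of symptom events that accompany a treated episode, 0.25 to 1; capture r = 0.9 with a triggered contact; capture k = 0.3 to 0.9 from scheduled contacts alone. The share of Arm 2 shocks that ATP would avert is approximated by a = 1 − 1/HR.

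Ratio = [p·r + (1−p)·k] / [p·((1−a)·r + a·k) + (1−p)·k]

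- HR 1.00: a = 0, ratio 1.00 throughout.
- HR 1.25: a = 0.20, ratio 1.00 to 1.15.
- HR 1.54: a = 0.35, ratio 1.00 to 1.30. The top value is 0.9 / (0.65 × 0.9 + 0.35 × 0.3) = 0.9/0.69 = 1.30.

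**5. Extreme case.** Assume that every ATP-ended episode would otherwise have been shocked and that no successful ATP is reported. Take ATP success s from the fast-VT trial in the Introduction: 0.72 adjusted, or 229/284 = 0.806. Assume 0.9 capture at a triggered contact and c = 0.5 or 0.8 at the next scheduled one. This is per episode-related symptom.

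- Arm 2 capture T = 1 − 0.1 × (1 − c) = 0.95 or 0.98.
- Arm 1 capture = (1 − s)·T + s·c.
- s = 0.72: 0.95/0.626 = 1.52 (c = 0.5); 0.98/0.850 = 1.15 (c = 0.8).
- s = 0.806: 0.95/0.587 = 1.62 (c = 0.5); 0.98/0.835 = 1.17 (c = 0.8).

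If half of the successful ATP episodes are reported, replacing s by s/2 gives 1.07 to 1.24.

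**The case against.** A reader might infer that the post-therapy contact is reserved for shocks, and hence that symptoms will be found more often in Arm 2, by 15% to 60%. The documents do not support that. The trigger wording covers ATP, a subject's report of ATP leads to the same contact, and the required patient-triggered alert is not tied to an arm. For subjects not on LATITUDE, the written trigger is the subject's report in both arms; the documents do not say how often successful ATP is noticed.

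The size is also open to challenge. The Introduction itself warns that reported ATP success may include much ATP given for non-sustained VT. Such episodes might end unshocked in Arm 2 and raise no alert there either. The 72% to 81% success comes from a trial with 18/24 detection (about 5.4 seconds), a 188 bpm cutoff and some secondary-prevention patients. This trial uses a 12-second delay, 200 bpm and primary prevention only. Under the plan's equal shock rates, the contacts balance.

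Finally, syncope is not a primary, secondary or tertiary outcome, and no by-arm syncope comparison is specified. Scheduled assessments in both arms can still find these events.

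All of this stands, and it limits the direction, size and consequence of the point. It does not remove the gap in the required alerts, nor does it supply an episode-linked symptom question at the scheduled call.

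**Conclusion.** The point holds as a risk of differential ascertainment in subjects on LATITUDE, confined to non-serious syncope and near-syncope. The mechanism is in the text, but its size is not. The apparent ratio is 1.0 if the arms have equal shock rates and about 1.0 to 1.3 at the equivalence margin. About 1.6 is an upper figure that needs both no reported ATP and every ATP-ended episode otherwise shocked. All these ratios rest on assumed capture probabilities. The device-recorded primary endpoint does not depend on this route, and deaths and serious events are reportable regardless of it. This is a modest, inexpensive improvement to safety data, and confidence in any particular size is low.

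**What to change.** In Sections 11.6, 11.7.1 and 11.7.2, put the same scripted syncope and near-syncope question to every subject in both arms at each scheduled contact. If dates are used as prompts, use all recorded ventricular episodes, whether or not treated, and do not name the therapy, so that the subject blinding in Section 11.4 is protected.

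Add one field to the adverse-event form for how the event was found: scheduled contact, post-therapy contact or spontaneous report. In by-arm syncope tables for the monitoring committee and the final report, make all events the main display and the split by detection route a sensitivity display. Using scheduled-contact events alone as the main display could hide real syncope associated with shocks.

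The cost is a few minutes at contacts that already exist and one form field. If dates are used, callers also need the episode list that the sponsor's LATITUDE team uploads. No visit, alert or device setting changes. Some recall delay remains, and subjects already questioned after a shock may be primed to report more.

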11.9. Device reprogramming outside of Investigational Plan

Once a subject is programmed to their respective randomized arm, every effort will be made to keep the subject's device programmed per the required programming in this protocol. Device reprogramming can be made if clinically indicated based on safety concerns. All device reprogramming changes, including the reason for change, must be recorded as a protocol deviation and the clinical circumstances must be documented as SAE or a device related adverse event, as applicable. After reprogramming to device settings outside of the required programming per protocol, subjects will remain in the assigned treatment arm until the end of the study to follow the methodology of intention-to-treat (ITT). Deviated programming doesn't qualify as reason for study withdrawal, and subjects will continue to be followed per the investigational plan.

